## Background

Dementia is among the most profoundly disabling and costly of all health conditions.(1) With devastating impacts and no known cure, health care is nevertheless pivotal to detection and treatment of behavioral symptoms and co-occurring medical conditions, initiation of social service referrals, and planning for future needs. Dementia poses special communication challenges in primary care(2-5) where most persons are initially treated.(6, 7) As persons with dementia have a high burden of co-occurring medical conditions,(1, 8, 9) communication challenges affect not only dementia diagnosis and treatment,(10, 11) but the care of other conditions, resulting in costly and burdensome treatments, inappropriate medication use, and potentially avoidable hospitalization.(12-17) Family caregivers play a vital role in dementia care, and are typically present and actively involved in medical visits.(18, 19) However, knowledge of how to optimize family caregiver involvement in medical visits is lacking.

This study will refine a brief intervention to effectively and purposely involve family caregivers (“companions”) who accompany persons with cognitive impairment to primary care visits. Existing evidence suggests that this focus is appropriate and potentially powerful. Nearly 4 in 10 patients attend primary care visits with a companion.(20, 21) These patients are older, in worse health, and more likely to have cognitive impairment than those who attend visits alone.(20-22) Companions are most often family members who not only attend visits,(20, 21) but actively participate in medical dialogue in varied ways that both help and hinder care.(21, 23, 24) Patients(25-27) and clinicians(28) strongly endorse involving family to meet the communication needs of patients who lack the capacity to obtain, process, and understand basic health information to make appropriate health decisions. However, *evidence-based strategies that specify how to involve family companions do not now exist.* Agenda-setting strategies (e.g., symptom checklists, question prompts) are a pragmatic approach to structure pre-visit preparations and increase patient involvement in care.(29, 30) However, few strategies target older adults,(31, 32) and **none** address the needs of persons with cognitive impairment and their accompanying family companions.

The study team has established proof of concept for a brief checklist to be used by older patients and their companions in the waiting room prior to medical visits. The checklist is designed to elicit and align patient and companion perspectives regarding patient health issues to discuss with the doctor, and to stimulate discussion about the companion's role in the visit. The premise for the checklist is that companions are typically motivated to support patients during medical visits, but that they often lack knowledge of the patient's health concerns and preferences for communication assistance. In a proof of concept randomized study of 32 patient-companion dyads, we found that the checklist was highly endorsed by patients, companions, and doctors. Analyses of audiotaped medical visits indicated that communication was significantly more patient-centered among patient-companion dyads who completed the checklist as compared with those who received usual care, and did not receive the checklist.(33) In post-visit surveys, doctors were 34% more likely to agree that intervention versus usual care companions "helped them provide good care to the patient" (94.1% vs. 60.0%; p=0.02). Intervention patients were more likely than usual care patients to agree that because their companion was present they "better understood their doctor's advice and explanations" (82.4% vs. 46.7%; p=0.03). However, *older adults with moderate and severe cognitive impairment were excluded in this early phase study.* Therefore, building on our preliminary work, this study seeks to refine and test the checklist to address the communication needs of older adults across a range of mild, moderate, and severe cognitive impairment.

## Study Aims

This study includes two specific Aims. The work associated with Specific Aim 1 was previously undertaken through a complementary study which was separately approved under IRB protocol 6194 ((34)). Although we restate the two specific Aims of this project for the sake of comprehensiveness, this proposal seeks approval for the work that pertains to Specific Aim 2.

**Aim 1. To refine a patient-companion checklist to address the communication needs of cognitively impaired older adults during primary care visits.** We will undertake an iterative user-centered design process to incorporate patient and companion feedback regarding checklist content and alternative delivery characteristics (optimal timing of delivery prior to the medical visit; whether the checklist is self-administered versus delivered by a facilitator) by undertaking in-depth interviews with older patients with mild, moderate, or severe cognitive impairment (n=20) and their companions (n=20; 20 dyads in total).

**Aim 2. To evaluate the feasibility of delivering the refined checklist to patients with cognitive impairment and their companions and to compare the checklist and control protocol with respect to patient centered communication (from visit audiotapes).** We will conduct a two-group pilot randomized trial to examine feasibility of the protocol and to compare medical communication during visits of patient-companion dyads who complete the checklist (n=50) with patient-companion dyads who receive usual care (n=50).

## Study Design

We will conduct a two group pilot randomized trial of up to 100 (50 per group) patients ages 65+ with cognitive impairment and their unpaid companion to test the effects of the refined checklist for medical communication. Each patient-companion dyad will be randomized to the intervention (to receive the checklist) or to a control protocol. Aim 2 has been designed as a pilot trial to evaluate the feasibility of delivering the study protocol to patients with cognitive impairment and their companions in primary care, and to generate preliminary evidence regarding the effect of the checklist on medical communication. For these reasons, the control group protocol will comprise usual care which is in this case existing clinical practice.(35, 36) Patients (when feasible), companions, and doctors in both intervention and control groups will complete in-person post-visit surveys immediately after the visit. Patients (when feasible) and companions will separately complete follow-up surveys by telephone two weeks after the doctor visit conducted by a research staff member. Because of high (100%) retention in our proof-of-concept study, we expect low dropout.

## Participants

We propose to enroll as many as 100 patient-companion dyads to provide us with information about the feasibility and acceptability of our study protocol, and preliminary insight regarding the effects of the intervention on medical

communication. We estimate that we will screen as many as 2,000 patients ages 65 and older to reach our target enrollment. In our proof of concept study 263 patients were screened and 32 (12.1%) patient-companion dyads were enrolled. As the Aim 2 pilot study will impose eligibility criteria pertaining to cognitive impairment, we have conservatively estimated that we will need to screen a larger number of older patients to attain recruitment goals than in our proof-of-concept study. However, we note that prevalence of mild cognitive impairment is not uncommon, and may be as high as 42% among older adults (37). The sample size of this study is based on practical factors related to available funding and duration of the R21 mechanism that is supporting this project.

Participants of this study will include three groups: (1) Older adult primary care patients with cognitive impairment, (2) Companions of older adult primary care patient study participants, and (3) primary care clinicians.

Inclusion/exclusion criteria for each of these groups are as follows:

- A. Older adult primary care patients. Inclusion criteria: 65 years or older, established patient of participating primary care clinician, regularly attend medical visits with one or more family member or unpaid friend “companion(s)”, agree to allow companion to be contacted and participate in the study, authorize disclosure of PHI in their electronic health record, able to provide informed consent or have a legally authorized representative. Exclusion criteria: younger than 65 years, no evidence of cognitive impairment, do not attend medical visits with family member or unpaid friend.
- B. Family companion. Inclusion criteria: Family member (spouse, adult child, parent, adult sibling) or unpaid friend who accompanies older adult participant to medical visits. Exclusion criteria: paid non-family member who accompanies patient to visits.
- C. Primary care clinicians. Inclusion criteria: practicing physician, nurse practitioner or physician assistant at a participating primary care practice.

## Recruitment

Primary care clinicians: Once IRB approval has been received, we will discuss the study with primary care clinicians who have an established practice at 3 primary care practices and we will invite them to participate. If a primary care clinician would like to participate they will be asked to provide written informed consent. We will track the number of primary care clinicians who are invited to participate and the number who agree to participate.

Older adult primary care patients and their companions: Patients will be recruited to the study in a phased process. Patients who are scheduled for an upcoming visit with a participating primary care clinician will be identified from the clinic schedule via electronic scheduling software by our research team. Patients will be mailed a letter informing them of the study. The letter will state that patients will receive a call in about 10 days to explain the study in greater detail. The letter will include a postcard that patients may return by mail if they would like to “opt-out” from learning more about the study. Patients who do not “opt-out” will be called by phone to inquire about their interest in learning more about the study. We will attempt no more than six calls to potentially eligible participants – but will leave no more than two voice messages at their place of residence. Patients who at the time of the phone call express an interest in participating will be asked questions to determine eligibility. Companions of eligible patients will be contacted by research staff to introduce the study, answer questions, and state that participation is voluntary. Companions who express interest in participating will be asked questions to determine eligibility. For patients with significant cognitive impairment who are unable to interact with study staff by telephone, eligibility will be assessed by completing the screening survey with a knowledgeable informant.

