## **Study Implementation**

We will partner with practicing primary care clinicians, established patients of participating clinicians, and patients' companions. Patient and companion eligibility will be ascertained by telephone by research staff. Written consent from patients and companions will be obtained immediately prior to a scheduled visit. After providing consent, enrolled patient-companion dyads will be randomly assigned to intervention or control group.

Patient-companion dyads who are assigned to the intervention group will be asked to complete a paper/pencil communication checklist to elicit topics they would like to discuss with their clinician during their visit and to discuss the patient/companion roles to be assumed. Patient-companion dyads assigned to the control group will receive usual care. Research staff will place two audio-recording devices in the exam room of all participating patient-companion dyads. The research staff will show patients, companions, and clinicians how to operate the audio-recording device and will state that the devices may be paused or stopped by the patient, companion, or clinician at any point during the visit. Upon completion of the visit research staff will retrieve the devices, collect the completed checklist from intervention group participants, and provide brief (10-15 minute) post-visit questionnaires to the patient and the companion to complete (separately) in the waiting room prior to leaving the office. Research staff will offer to assist reading and/or completing the questionnaires to patients or companions who request assistance. Clinicians will be asked to complete a brief survey of questions relating to patient health and patient/companion behavior during the visit. Two weeks after the visit, research staff will telephone patients and companions separately to complete a brief (20 minute) telephone survey. Patients and companions will each be compensated with a \$25 gift card for the in-person interview and with a \$25 gift card for the telephone interview (up to \$50 total) for their time.

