## **Participant Assignment**

Each patient-companion dyad will be randomized to treatment or control group in a 1:1 ratio using stratified, blocked randomization by doctor with alternating block sizes of 4 and 6 for each clinician. A statistical program, developed by the project statistician and unknown to study staff will be used to prospectively generate random treatment group assignment of study participants for each participating clinician. A set of opaque envelopes will be prepared for each clinician following the results of the statistical program. Upon providing informed consent, research staff will open the next sequentially ordered envelope specifying treatment group by clinician. Patient-companion dyads assigned to

the treatment group will receive a copy of the pre-visit checklist and a clipboard and pen. Patient-companion dyads assigned to the control group will receive care as usual. Participants and research staff responsible for the randomization protocol at the enrollment visit will be aware of participant assignment status after it occurs. The PI, project statistician, and research staff responsible for coding study outcomes will be blinded throughout the study. As randomization occurs at the level of the patient-family dyad, clinicians will care for patients in both groups. Clinicians will be blinded to group assignment.

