The primary outcome of the Aim 2 trial is an objective composite measure of visit medical communication that will be constructed from RIAS-coded categories. This outcome, *patient-centered communication*, is a ratio of statements that encompass psychosocial and socio-emotional elements of medical dialogue that reflect the lived experience of patients (in the numerator), in relation to statements that are more biomedical and disease-focused (in the denominator).(23, 40) Higher values ( $>1$ ) indicate more patient-centered encounters and lower values ( $<1$ ) indicate more doctor-centered encounters. Prior work indicates the measure has predictive and concurrent validity in relation to consequential patient and doctor outcomes.(23, 40, 44, 45) We will additionally examine several secondary outcomes of visit processes (e.g., visit duration and verbal activity of patients, companions, and doctors, from audiotapes) and *discussion of memory* from audiotapes. Acceptability will be evaluated from responses to the agenda setting checklist by intervention dyads. Measures of patient-companion concordance will be constructed to indicate whether each health issue was selected as a priority by the patient only, companion only, neither, or both. From companion responses to post-visit surveys we will assess how the checklist was completed (patient only, companion only, together) and how long it took to complete the checklist. The utility, burden, and helpfulness of the checklist will be assessed in written post-visit surveys using questions from our formative work. (33) Additional measures. From patients' electronic health record we will assess age, gender, and diagnosis of cognitive impairment or dementia at the time of the enrollment visit. Cognitive function will be measured using the Mini-Mental State Examination (MMSE)(41) which will be administered to patients by research staff immediately after the enrollment visit. From telephone interviews we will assess patient race/ethnicity, living arrangement, educational attainment, receipt of help with self-care and household activities, and numbers of daily prescribed medications. Measures of companion characteristics will include relationship to the patient, gender, self-rated health, and educational attainment, from

follow-up telephone interviews. We will assess clinician characteristics (age, gender, specialty training, and years in practice) from baseline surveys administered at the time of informed consent.

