## Analysis

Analyses will be performed in SAS statistical software, with each patient-companion dyad and their recorded visit as the unit of analysis. In this two-group randomized pilot trial, we will compare the effects of the refined checklist on medical communication among up to 100 (50 per group) patients ages 65+ with cognitive impairment and their companion. Simple statistics (frequency distributions, group means) will be used to assess potential differences between eligible patients willing and unwilling to participate, between enrolled participants assigned to intervention and control groups, and process measures relating to completion of the agenda setting intervention. We will rely on established cut-points and approaches to constructing primary and secondary outcome measures, as well as measures of patient and companion attributes that will serve as control variables (socio-demographic characteristics, health status, aspects of the patient and companion relationship). We will rely on established cut-points of the Mini-Mental State Examination test to categorize patient participants as having mild (scores of 20-25), moderate (scores of 10-20) or severe (scores of less than 10) cognitive impairment.(41, 42) We will primarily evaluate the consistency, direction, and magnitude of differences in study outcomes by undertaking analyses that are stratified by intervention group (checklist versus usual care) and for the subgroups of patient cognitive function (mild, moderate, or severe, based on the Mini-Mental State Examination cut-points). Intervention effects on primary and secondary outcomes will be examined using regression models in which the main independent variable is treatment assignment. We will use generalized estimating equations (PROC GENMOD in SAS, version 9.4 (SAS Institute, Cary North Carolina)) to assess the direction, magnitude, and statistical significance of between-group differences in outcomes. The generalized estimating equations method will be used because it accounts for within-clinician clustering of patients and the different numbers of enrolled patient-companion dyads per clinician.(46) An exchangeable correlation structure will be assumed. Regression models will include treatment assignment (agenda setting versus usual care) and patient-level covariates that are postulated as affecting communication, such as age, gender, and cognitive function. We will evaluate recruitment, retention, and the timeliness and completeness of collected data,(47) as well as checklist acceptability (utility, burden, helpfulness) using questions from our formative work. (33) The statistical significance of patient-companion concordance/discordance on priorities for the visit agenda will be assessed with McNemar's test. We recognize the need for caution in interpreting pilot trial results. We will evaluate recruitment and dropout rate as well as effect size of primary and secondary outcomes to help inform the design and sample size calculations for a larger trial. We will examine similarities and differences in pilot trial results and our initial proof-of-concept study. The ultimate goal of the Aim 2 pilot trial is to demonstrate the feasibility of implementing the study protocol among primary care patients with a range of cognitive impairment and their companion and to glean insight regarding effects of the refined checklist for medical communication.

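### Booked visit type and slot length are fixed before randomisation but neither recorded nor adjusted for, so a cheap gain in precision, mainly for visit duration and verbal activity, goes unused

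*Combined protocol and SAP*

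**What the plan says.** The Recruitment section starts from appointments that already exist: patients who have one coming up "will be identified from the clinic schedule via electronic scheduling software by our research team". Written consent is taken immediately before that visit (Consent Process, Study Implementation), and allocation comes next: "After providing consent, enrolled patient-companion dyads will be randomly assigned to intervention or control group". So the type and length of the booked appointment are settled before the arm is known.

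Balance is sought on clinician only, through "stratified, blocked randomization by doctor with alternating block sizes of 4 and 6 for each clinician" (Participant Assignment).

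The primary ratio and the secondary visit-process outcomes come from one recorded visit. The secondary outcomes include "visit duration and verbal activity of patients, companions, and doctors, from audiotapes" (Measurement), and Table 1 lists duration in minutes. Table 1 has no row for scheduled visit type, reason for visit or slot length.

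The Analysis section describes its control variables as "socio-demographic characteristics, health status, aspects of the patient and companion relationship". Its GEE models contain treatment and "patient-level covariates that are postulated as affecting communication, such as age, gender, and cognitive function". No property of the visit as booked is named.

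**The concern.** The plan accepts the principle of adjusting for baseline factors thought to affect communication, and it takes the dyad with its recorded visit as the unit of analysis. It then records only attributes of the people and nothing about the visit as booked. Slot length plausibly influences how long a visit lasts and how much is said. It may also influence the psychosocial to biomedical mix, though less clearly.

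Where a clinician sees participants in slots of different kinds, that variation goes into the residual. What is at stake is precision. The sample is capped by funding (Participants), so precision cannot be bought with more dyads, and the pilot's effect sizes are meant to inform the sample size of a larger trial (Analysis). A field that is not collected cannot be used later, even though the covariate list is open.

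**Working it through.** The documents give no power calculation, SD or slot mix, so there is no stated figure to reproduce. Every size below rests on assumptions.

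**From the documents:** up to 100 dyads, 50 per arm, allocated 1:1 and stratified by clinician.

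**Assumed:** share of visits in a longer slot p = 0.30 to 0.40; within-slot SD of actual duration s = 7 to 8 minutes; difference in actual mean duration between slot types d = 5 to 10 minutes. The upper end corresponds, for example, to 20- versus 30-minute slots whose actual durations differ by the full scheduled 10 minutes. The lower end has the same slots differing by half that.

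**Formulas (linear model):**
- R-squared = p(1−p)d² / [p(1−p)d² + s²]
- Fall in standard error = 1 − √(1 − R-squared)
- Equivalent extra dyads = 1/(1 − R-squared) − 1

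| d (min) | p | s (min) | R-squared | Fall in SE | Equivalent extra dyads |
|---|---|---|---|---|---|
| 5 | 0.30 | 8 | 5.25/69.25 = 0.076 | 4% | 8% |
| 5 | 0.40 | 7 | 6/55 = 0.109 | 6% | 12% |
| 10 | 0.30 | 8 | 21/85 = 0.247 | 13% | 33% |
| 10 | 0.40 | 7 | 24/73 = 0.329 | 18% | 49% |

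These R-squared values should be read as the share explained within clinicians. If slots differ mainly between clinicians, the gain is smaller.

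**Primary ratio.** Visit length partly cancels in a ratio, so any gain must come from visit type shifting the mix of talk. With an assumed R-squared of 0.05 to 0.15, the fall in SE is 1 − √0.95 = 2.5% to 1 − √0.85 = 8%, equal to about 5% to 18% more dyads.

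**Chance imbalance against the standard error.** Take p = 0.40 and d = 10. The unadjusted SD is √(24 + 49) = 8.5 to √(24 + 64) = 9.4 minutes. Multiplying by √(2/50) = 0.2 gives a standard error of 1.7 to 1.9 minutes for the difference between arms. The arms differ in slot mix by 16 points or more in 12.5% of trials (two independent binomial counts) or 15% (exactly 40 long slots among 100, split at random); both ignore clinician blocking. An imbalance of 16 points shifts the difference by 0.16 × 10 = 1.6 minutes, which is less than one standard error. The ordinary confidence interval already allows for it.

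**The case against.** The strongest case is that nothing here is wrong. A reader might infer that an uneven split of long and short appointments would bias the trial, or pass for a checklist effect. The documents do not support that: allocation is random and concealed in opaque envelopes, and the unadjusted standard error includes this source of chance variation, as the 1.6-minute example shows.

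A reader might also infer that any kind of appointment can enter. In fact patients must be established with the clinician (Participants), they are mailed a letter and called about 10 days later (Recruitment), and the encounter is a regularly scheduled office visit (Study Implementation). New-patient and same-day visits are therefore largely filtered out. Clinician stratification and the GEE clustering deal with differences between clinicians' schedules, and the documents do not show how much slots vary within a clinician.

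All of that stands, and it may put the gain towards the lower end of the range. The point that the covariate list is given only by way of example stands in part: adjustment is not ruled out, but the list is confined to patient-level factors and the booking field is not among the planned measures. It also stands that age and gender are not the only named covariates, since cognitive function is named too. Nothing in the documents shows that slot length would explain more than these do.

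**Conclusion.** A cheap improvement that the plan leaves unused, not an error. On the stated assumptions, adjusting for the booked slot would cut the standard error for visit duration by about 4% to 18%, equal to about 8% to 49% more dyads. The top of that range requires actual durations to differ by the full 10 scheduled minutes, so it should not be quoted alone. Verbal activity should benefit in the same direction by an amount the documents cannot fix. For the primary ratio the gain is modest, 2.5% to 8% of the standard error on an assumed R-squared. The formula does not carry over to discussion of memory if that is coded yes/no: adjustment in a logistic model changes the odds ratio being estimated and need not reduce its standard error. Slot mix, SDs and R-squared are all assumptions. So is a usable, comparable slot field in the software at all three practices; the Recruitment section says only that the software is used to identify patients.

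**What to change.** 1. Copy scheduled visit type and slot length from the scheduling software, as booked, before the envelope is opened, and add both to Table 1.
2. Pre-specify one of them (slot length, or a two-level visit type) as a covariate in the GEE models for visit duration and verbal activity, and in the model for the primary ratio with a modest expected gain.
3. Report the distribution by arm. For discussion of memory, if coded yes/no, show that distribution without claiming the same gain in precision.
4. Do not adjust for actual visit duration, which is a post-randomisation outcome.

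Covariate adjustment is more practical than a second stratification factor. With blocks of 4 and 6 within clinician and at most 100 dyads, further strata would leave many incomplete blocks.

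The cost is a small addition to data collection from software already in use and 1 to 2 degrees of freedom in each model. If slots prove uniform, the loss is negligible.
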